4.2.3. Modified Intent-to-Treat Population

A subject who was randomized in Stage 1, consented to participate in Stage 2, and has at least 1 valid and determinate assay result related to the proposed analysis during Stage 2 will be included in the mITT population. The immunogenicity results based on the mITT population will be summarized according to the vaccination as randomized. Since Stage 2 is entirely exploratory, analysis of immunogenicity results based on the mITT population will be considered supportive and will be performed only if requested.

4.3. RSV Vaccine Month-0, Month-2 Cohort

4.3.1. Safety Population

All subjects receiving at least 1 dose of the investigational products (RSVpreF 240 µg + CpG/Al(OH)₃ or placebo) at Visit 1 will be included in the safety population for this cohort. For the safety analyses, subjects will be analyzed according to the investigational product received. The safety population will be the only analysis population for safety evaluation included in this study cohort.

4.3.2. Evaluable Immunogenicity Population

This evaluable immunogenicity population will include subjects who:

- Are eligible (have signed informed consent and met all inclusion/not met any exclusion criteria) and were randomized into the study;
- Have received both vaccinations at Months 0 and 2 as randomized;
- Have a Visit 4 (1 month after Vaccination 2) blood draw for assay testing within 27 to 42 days after Visit 3, inclusive (after vaccine administration) (note: the 27- to 42-day interval is calculated as the Visit 4 date minus the Visit 3 date);
- Have at least 1 valid and determinate assay result for the proposed analysis;
- Have no major protocol violation as determined by the study clinician.

Major protocol violations will be determined as described in [Section 4.1.2](#) by clinical review.

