9.2.1.3. RSV Vaccine Month-0, Month-2 Cohort

- **Evaluable immunogenicity population:** In general, the subject must have been eligible for the study, have received all vaccinations to which the subject was randomized, have had blood drawn within the prespecified time frames at the 1-month post-Vaccination 2 follow-up visit, have at least 1 valid and determinate assay result for the proposed analysis, and have no other major protocol violations.
- **mITT population:** A subject must have been randomized and have at least 1 valid and determinate assay result related to the proposed analysis.

The immunogenicity data will be summarized according to the vaccine as received for the evaluable immunogenicity population and as randomized for the mITT population. The evaluable immunogenicity population will be the primary analysis population for immunogenicity results.

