4.1.2. Evaluable Immunogenicity Population

This analysis population will include subjects who:

- Are eligible (have signed informed consent and met all inclusion/not met any exclusion criteria) and were randomized into the study;
- Have received both the SIIV and RSV vaccine or placebo and SIIV as randomized;
- Have a Visit 2 (1 month after vaccination) blood draw for assay testing within 27 to 42 days after Visit 1 (after vaccine administration) (note: the 27- to 42-day interval is calculated as the Visit 2 date minus the Visit 1 date);
- Have at least 1 valid and determinate assay result for the 1-month post-Vaccination 1 visit;
- Have no major protocol violation as determined by the study clinician.

Major protocol violations will be determined by clinical review. A major protocol violation is a protocol violation that, in the opinion of the sponsor's study medical monitor, would materially affect assessment of immunogenicity, eg, subject receipt of a prohibited vaccine or medication that might affect immune response or a medication error with suspected decrease in potency of the vaccine. The sponsor's medical monitor will identify those subjects with protocol violations before any immunogenicity analysis is carried out.

The evaluable immunogenicity population will be the primary analysis population for the immunogenicity endpoints evaluated among this cohort. Subjects will be included in the vaccine group as randomized in the analysis, which, by the population definition, is equivalent to the vaccine group corresponding to the vaccine received.

The evaluable immunogenicity population will also be the primary analysis population for the cellular assay results reported from this cohort.

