6.2.1.2. Additional Analysis

For the Primary Study Cohort - Stage 1, GMTs at all other applicable visits after Vaccination 1 but before Vaccination 2 will be summarized along with associated 2-sided 95% CIs, by vaccine group, for both RSV A– and RSV B–neutralizing antibody titers.

Similarly, for the RSV Vaccine Month-0, Month-2 Cohort, GMTs at all applicable visits will be summarized with 2-sided 95% CIs.

For the Primary Study Cohort - Stage 2, GMTs at all applicable visits (including visits in Stage 1 and Stage 2) will be summarized with 2-sided 95% CIs.

It should be noted that the inclusion of each applicable blood sampling visit will not take the protocol-required visit window into consideration as long as subjects meet the evaluable immunogenicity population criteria.

Additionally, all fold rises specified in [Section 3.2.1](#) will be summarized with GMFRs and associated 2-sided 95% CIs.

The following comparisons will be made in order to:

1. Assess adjuvant effects:

For the Primary Study Cohort - Stage 1, GMTs at each post–Vaccination 1 visit will be compared between RSVpreF 240 µg + Al(OH)₃ + SIIV and RSVpreF 240 µg + SIIV; as well as between RSVpreF 240 µg + CpG/Al(OH)₃ + SIIV and RSVpreF 240 µg + SIIV. GMRs and associated 2-sided 95% CIs will be calculated for each post–Vaccination 1 visit in Stage 1.

2. Assess SIIV coadministration interference to immune response induced by RSVpreF 240 µg + CpG/Al(OH)₃:

This will combine 1-month post-Vaccination 1 NT data from the **Primary Study Cohort - Stage 1** and the **RSV Vaccine Month-0, Month-2 Cohort**.

GMTs at 1 month after Vaccination 1 for RSV A NT and RSV B NT will be compared between the RSVpreF 240 µg + CpG/Al(OH)₃ with SIIV group (**Primary Study Cohort - Stage 1**) and the RSVpreF 240 µg + CpG/Al(OH)₃-only group (**RSV Vaccine Month-0, Month-2 Cohort**). GMRs and associated 2-sided 95% CIs will be calculated.

For the 1-month postvaccination visit, GMT summaries from the **Primary Study Cohort - Stage 1** and the **RSV Vaccine Month-0, Month-2 Cohort** will be presented for each vaccine group together with pooled placebo data.

Analysis using the mITT population may be used if there is a large enough difference compared with the evaluable immunogenicity population.

Figures:

For the remaining 2 cohorts (Primary Study Cohort - Stage 2 and RSV Vaccine Month-0, Month-2 Cohort), RCDCs will be plotted for prevaccination and 1-month postvaccination visits only.

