6.3.3. Anti-RSV Prefusion F IgG

For each cohort, the IgG A and IgG B will be descriptively summarized with GMC and associated 2-sided 95% CI, at each applicable visit among the evaluable immunogenicity population ([Section 6.2.1](#)).

Similarly, for each cohort, the fold rise of IgG A and IgG B (defined in [Section 3.3.2](#)) will be descriptively summarized with GMFR and associated 2-sided 95% CI, at each applicable visits among the evaluable immunogenicity population.

GMCs at 1 month after Vaccination 1 for IgG A and IgG B will be compared between the RSVpreF 240 µg + CpG/Al(OH)₃ with SIIV group (**Primary Study Cohort - Stage 1**) and the RSVpreF 240 µg + CpG/Al(OH)₃-only group (**RSV Vaccine Month-0, Month-2 Cohort**). GMRs and associated 2-sided 95% CIs will be calculated.

For the 1-month postvaccination visit, a GMC summary from the **Primary Study Cohort - Stage 1** and the **RSV Vaccine Month-0, Month-2 Cohort** will be presented for each vaccine group together with pooled placebo data.

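### The Month-0/Month-2 evaluable set is tied to dose 2 and Visit 4 but is also used for the dose-1 comparison with Stage 1, so the two sides follow different selection and timing rules

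*SAP*

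**What the plan says.** **Month-0/Month-2 cohort.** SAP 4.3.2 asks for eligibility and randomization, no major protocol violation, and receipt of the two assigned doses. Its only blood-draw criterion concerns the second dose: "Have a Visit 4 (1 month after Vaccination 2) blood draw for assay testing within 27 to 42 days after Visit 3, inclusive". Its assay criterion is not tied to a particular visit: "Have at least 1 valid and determinate assay result for the proposed analysis". Protocol 9.2.1.3 ties the set to the same visit ("have had blood drawn within the prespecified time frames at the 1-month post-Vaccination 2 follow-up visit") and makes the evaluable population primary for immunogenicity.

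**Stage 1.** SAP 4.1.2 applies the same general criteria but anchors the set on the first dose: "Have a Visit 2 (1 month after vaccination) blood draw for assay testing within 27 to 42 days after Visit 1", with a valid result at that visit.

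**Where the two sets meet.** SAP 6.2.1.2 assesses the effect of the seasonal influenza vaccine (SIIV) on the response to 240 µg RSV vaccine with CpG/Al(OH)₃ by combining the two cohorts: "GMTs at 1 month after Vaccination 1 for RSV A NT and RSV B NT will be compared between the" group given SIIV in Stage 1 and the group given no SIIV in the Month-0/Month-2 cohort. SAP 6.3.3 repeats this for IgG: "GMCs at 1 month after Vaccination 1 for IgG A and IgG B will be compared between the" same two groups. Both sections also show the 1-month results with pooled placebo.

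**Timing of other visits.** SAP 6.2.1.2 relaxes visit timing for anyone who qualifies for the evaluable set: "the inclusion of each applicable blood sampling visit will not take the protocol-required visit window into consideration as long as subjects meet" its criteria.

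**Alternatives.** SAP 4.4 rules out further analysis sets. For this cohort, SAP 4.3.3 runs the mITT analysis only on request. SAP 6.2.1.2 says mITT may be used if the difference from the evaluable set is large enough, and gives no threshold.

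**The concern.** A dose-1 result is complete once the Visit 2 sample has been drawn and assayed. In one cohort, whether that result counts depends on what happens afterwards: receipt of dose 2 about two months in, and a draw about a month after that. In the other cohort it does not. Conversely, the Visit 2 draw date decides entry into the Stage 1 set and plays no part in the Month-0/Month-2 set.

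These are the two sides of the SAP's only comparison of the RSV response with and without SIIV. Describing the response to the first dose is also a stated objective of the Month-0/Month-2 cohort, and SAP 7.2 says the interim results will guide the choice of dose, formulation and schedule. The comparison already crosses separately enrolled cohorts. An avoidable difference in who is counted and when they were sampled could add to, or hide, an apparent SIIV effect.

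**Working it through.** **1. The rules side by side**

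| Requirement for the dose-1 contrast | Stage 1 (SAP 4.1.2) | Month-0/Month-2 (SAP 4.3.2) |
|---|---|---|
| Eligible, randomized, no major violation | yes | yes |
| Dose 1 as randomized | yes | yes |
| Dose 2 as randomized | no | yes |
| Visit 2 draw 27-42 days after Visit 1 | yes | no |
| Visit 4 draw 27-42 days after Visit 3 | no | yes |
| Valid result | at the 1-month visit | for the proposed analysis |

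- *On-time Visit 2 sample at day 30, dose 2 not received or Visit 4 missed or out of window:* the Month-0/Month-2 subject is excluded. A Stage 1 subject with the same dose-1 sample is included.
- *Visit 2 sample outside 27-42 days, later visits in order:* the Month-0/Month-2 subject is included. A Stage 1 subject is excluded.

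Protocol 6.3.4 rechecks the temporary-delay criteria at Visit 3, and Protocol 7.4 pauses RSV vaccination when a stopping rule is met, so a missed dose 2 can arise from routine conduct.

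**2. Inputs for size**

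The plan gives no figure for this point: no titer SD, loss rate or mistiming rate. The group size is stated as about 31 (Protocol Table 4) and is consistent: 250/8 = 31.25 and 62/2 = 31. Everything else below is assumed.

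**3. Selective loss**

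Assume k of 31 are excluded, their mean log titer differs by d SDs from those retained, and the natural-log SD is s. Then GMT(retained)/GMT(all) = exp(∓(k/31)·d·s), with minus if the excluded titers are higher.

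| k | d | s | (k/31)·d·s | Excluded higher | Excluded lower |
|---|---|---|---|---|---|
| 3 | 0.5 | 0.8 | 0.039 | 0.96 | 1.04 |
| 3 | 1 | 1.2 | 0.116 | 0.89 | 1.12 |
| 6 | 0.5 | 0.8 | 0.077 | 0.93 | 1.08 |
| 6 | 1 | 1.2 | 0.232 | 0.79 | 1.26 |

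The arm's GMT is thus 4-21% too low or 4-26% too high. If d = 0, the expected shift is zero.

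**4. Precision**

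With the two-sample t interval of SAP 5.2.2.3, the log-scale half-width grows by √[(1/31 + 1/(31−k))/(2/31)] times the ratio of t quantiles.

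- k = 3: 1.026 × (2.002/2.000) = 1.03.
- k = 6: 1.058 × (2.005/2.000) = 1.06.

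For scale, with 31 per arm the interval runs from the GMR divided by to the GMR multiplied by exp(2.000·s·√(2/31)). That factor is 1.50 at s = 0.8 and 1.84 at s = 1.2.

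**5. Mistimed samples**

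Take an extreme case: a Visit 2 sample at day 54 instead of day 31, with an assumed titer half-life h of 60-180 days.

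- The sample's own ratio is 0.5^(23/h): 0.77 at h = 60 and 0.92 at h = 180.
- Its effect on the arm's GMT is that ratio to the power 1/31: 0.991 and 0.997, a drop of 0.9% or 0.3%.
- Six such samples give 0.95 and 0.98.

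**The case against.** **One fixed set is a defensible choice.** The cohort exists to study a two-dose regimen. A single set keeps the post-dose-1, pre-dose-2 and post-dose-2 titers, and the dose-1-to-dose-2 fold rise in SAP 3.2.1, on largely the same subjects. Within the cohort both randomized arms face the same rule. This stands for the post-dose-2 and paired results. It does not extend to a dose-1 contrast with another cohort.

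**The comparison is weak anyway.** It is exploratory, descriptive and non-randomized. Stage 1 enrolled in April-June 2019, and the other cohort was added by Amendment 3. That limits the severity, but it is no reason to add a removable difference.

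**Other criteria offer some protection.** Protocol 6.3.3 schedules Visit 2 at 28-35 days, so draws are windowed in conduct. Clinical review can also remove deviations that materially affect immunogenicity. Neither is an analysis criterion for Visit 2 timing, and the window waiver in SAP 6.2.1.2 points the other way. The optional mITT analysis would restore dropped subjects but would not remove mistimed draws.

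**The population is partly inferred.** The comparison paragraphs do not name one. It follows from the surrounding text of SAP 6.2.1.2 and 6.3.3 and from Protocol 9.2.1.3. I think the reading is secure.

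**Stronger readings that the documents do not support:**

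- *That a delayed dose 2 by itself excludes a subject.* SAP 4.3.2 sets no day window for Visit 3. Delay excludes only if the reference to Months 0 and 2 is read strictly or the review calls it a major violation.
- *That a violation after Visit 2 counts in one cohort only.* SAP 4.1.2 sets no time cutoff either, and SAP 4.3.2 refers back to the same review.
- *That mistiming could move the contrast by 8-23%.* That is the change in one sample under the assumed waning. Day 54 is also the first day of the Visit 3 window, when a separate pre-dose draw is already scheduled.

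**Conclusion.** The mismatch is real and follows from the text: the two sides of the dose-1 SIIV-interference ratio, and of the pooled-placebo summary, are selected and timed under different rules.

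A reader might infer that the ratio is biased, or biased in a known direction. The documents do not support that. They give no count of affected subjects, and the excluded could have higher, lower or similar titers. The 4-21% downward and 4-26% upward shifts rest on assumed losses of 3-6 of 31 and an assumed difference of 0.5-1 SD. The loss of precision (3-6%) is minor, and one mistimed sample moves the arm by under 1%. Even the largest assumed shift is smaller than the sampling uncertainty of the ratio at this group size.

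This is worth correcting because the correction is cheap. It does not undermine the study: no hypothesis test depends on it, and the primary safety endpoints use the safety population.

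**What to change.** In SAP 4.3.2, add a dose-1 evaluable population for the Month-0/Month-2 cohort that mirrors SAP 4.1.2:

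- eligible and randomized;
- Vaccination 1 received as randomized;
- Visit 2 draw 27-42 days after Visit 1;
- valid and determinate Visit 2 result;
- no major violation, with the same time cutoff for violations stated for Stage 1 and Month-0/Month-2.

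Name this population in SAP 6.2.1.2 and 6.3.3 for the cross-cohort dose-1 ratios, the pooled-placebo summary and the cohort's Visit 2 dose-1 summaries. Keep the current set for post-dose-2 results and for paired dose-1-to-dose-2 fold rises. Amend the count of populations in SAP 4 and the statement in SAP 4.4 to match.

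The cost is SAP wording and one population flag, with no new data or visits. Protocol 9 lets the SAP modify analyses other than major changes to the primary endpoints. SAP 4 requires population membership to be settled before unblinding; if that point has passed, report the added set as post hoc. The one drawback is that N will differ between this cohort's dose-1 and dose-2 tables, which a footnote can explain.

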4.3.3. Modified Intent-to-Treat Population

All randomized subjects included in this cohort who have at least 1 valid and determinate assay result related to the proposed analysis will be included in the mITT population. The immunogenicity results based on the mITT population will be summarized according to the vaccination as randomized. Since this cohort is entirely exploratory, analysis of immunogenicity results based on the mITT population will be considered supportive and will be performed only if requested.

CCI

PFIZER CONFIDENTIAL

4.4. Other Analysis Sets

No other analysis sets will be defined in this study.

5. GENERAL METHODOLOGY AND CONVENTIONS

5.1. Hypotheses and Decision Rules

5.1.1. Statistical Hypotheses

This Phase 1/2 study is designed to describe the safety, tolerability, and immunogenicity of the RSV vaccine alone or formulated with Al(OH)₃ or CpG/Al(OH)₃, when administered concomitantly with SIIV, and a 240-μg dose of the RSV vaccine with CpG/Al(OH)₃, but without SIIV. No formal statistical hypothesis testing will be performed. An estimation approach will be used to assess the safety and immunogenicity objectives.

5.1.2. Statistical Decision Rules

Statistical decision rules will not be utilized in this study. All analyses are considered descriptive in nature.

5.2. General Methods

Safety data, immunogenicity data, and cellular assay data will be summarized by vaccine group for each cohort. All analyses will be descriptive in nature.

5.2.1. Analyses for Binary Data

Descriptive statistics for binary variables are the proportion (%) and the numerator (n) and the denominator (N) used in the proportion calculation. The 2-sided 95% CI for percentage, and for difference in percentages, will also be presented, where appropriate.

1. The 2-sided 95% CI for the proportion will be constructed by the Clopper-Pearson method described by Newcombe.³ The 2-sided 95% CI will be presented in terms of percentage.
2. The 2-sided 95% CI for the difference in the proportions may be computed using the Chan and Zhang method.⁴ The 2-sided 95% CI will be presented in terms of percentage. This may be used for some exploratory analyses.

5.2.2. Analyses for Continuous Data

Unless otherwise specified, descriptive statistics for continuous variables are n, mean, median, standard deviation, minimum, and maximum.

The CI for the mean of the continuous variable will be constructed by the standard method based on Student's t distribution.

5.2.2.1. Geometric Mean Titer

Continuous immunogenicity endpoints will be logarithmically transformed for analysis. Geometric mean titer (GMT) or geometric mean concentration (GMC) and associated 2-sided 95% CI will be calculated at each available time point for each vaccine group and cohort. Geometric means and their 2-sided 95% CIs will be derived by calculating means and CIs on the natural log scale based on the t distribution, then exponentiating the results.

5.2.2.2. Geometric Mean Fold Rise

Geometric mean fold rises (GMFRs) will be limited to subjects with nonmissing values at both visits. Individual subject antibody-level fold rise from one time point to another time point will be transformed in natural logarithm scale for analysis. Means and their 2-sided 95% CIs on the natural log scale will be based on the 1-sample Student's t distribution. GMFRs and corresponding 2-sided 95% CIs will be calculated by exponentiating the results from the natural log scale.

5.2.2.3. Geometric Mean Ratio

The geometric mean ratio (GMR) will be calculated by transforming the group mean difference of the antibody levels in natural logarithm scale to original scale. Two-sided 95% CI is also computed by exponentiating the CIs from the natural log scales using 2-sample Student's t distribution for the mean difference of measures on the logarithmically transformed assay results.

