9.2.2. Analysis of Immunogenicity Endpoints

Continuous immunogenicity endpoints will be logarithmically transformed for analysis. Geometric mean titers (GMTs) and associated 2-sided 95% confidence intervals (CIs) will be calculated at each available time point for each vaccine group and cohort. CIs will be calculated by back transformation of the CIs for the mean of the logarithmically transformed assay results computed using Student's t distribution.

Geometric mean fold rises (GMFRs) and associated 2-sided 95% CIs will be provided for RSV A- and RSV B-neutralizing antibody titers from before vaccination to each available time point after vaccination for each vaccine group and cohort. The GMFR will be calculated as the mean difference of individual subject logarithmically transformed antibody levels (postvaccination minus prevaccination) and back transformed to the original units.

Two (2)-sided 95% CIs are also computed by back transformation of the CIs using 1-sample Student's t distribution for the mean difference of measures on the logarithmically transformed assay results.

To assess whether concomitant administration of RSV and influenza vaccines interferes with the immune response to SIIV, geometric mean ratios (GMRs) and associated 2-sided 95% CIs will be calculated for HAI strains in SIIV by comparing sera drawn from subjects vaccinated with SIIV concomitantly with, for example, RSV vaccine 60 µg + CpG/Al(OH)₃ to sera drawn from subjects vaccinated with SIIV alone at 1 month after vaccination. This analysis will also be done for the other formulations and dose levels of RSV vaccine. The GMR will be calculated as the group mean difference of logarithmically transformed antibody levels and back transformed to the original units. Two (2)-sided 95% CIs are also computed by back transformation of the CIs using 2-sample Student's t distribution for the mean difference of measures on the logarithmically transformed assay results.

Seroprotection in HAI titers is defined as the percentage of subjects achieving a HAI antibody titer $\geq 1:40$. The percentage of subjects achieving a seroprotection at 1 month after vaccination will be computed for each virus strain contained in SIIV separately.

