RSV Vaccine Month-0, Month-2 Cohort. Approximately 62 RSV vaccine-naïve subjects were to be randomized 1:1 to receive either 240 µg of RSV vaccine with CpG/Al(OH)₃ or placebo at Visit 1 (Month 0). At Visit 3 (Month 2), subjects will receive a second dose of RSV vaccine or placebo as randomized at Visit 1. No concomitant SIIV will be given.

Key safety data collected for all study subjects in all cohorts include electronic diary (e-diary) reports of local reactions and systemic events that occur in the 14 days after each vaccination visit (RSV vaccine or placebo). Serious adverse events (SAEs) are being collected for all subjects from informed consent until study completion. Adverse events (AEs) are collected from informed consent until 1 month after the Vaccination 1 visit (for Stage 1); from reconsent until 1 month after the Vaccination 2 visit (for Stage 2); and from informed consent until 1 month after the Vaccination 2 visit (for the RSV Vaccine Month-0, Month-2 Cohort). Medically attended AEs (MAEs) are collected after the AE collection period. AEs occurring up to 48 hours after blood draws are also collected. An internal review committee (IRC) and an external data monitoring committee (E-DMC) will monitor safety in this study.

Blood samples are collected from all subjects for antibody testing. For Stage 1 subjects, blood samples were taken before Vaccination 1 and 1, 3, 6, and 12 months after Vaccination 1. For Stage 2 subjects, blood samples for antibody testing are collected before Vaccination 2 and 1, 3, 6, and 12 months after Vaccination 2. For the RSV Vaccine Month-0, Month-2 Cohort, blood samples for antibody testing are collected before Vaccination 1, 1 month after Vaccination 1, before Vaccination 2, and 1, 6, and 12 months after Vaccination 2.

A subset of study subjects in all cohorts will have additional blood taken for cellular assays (peripheral blood mononuclear cells [PBMCs]). For Stage 1 subjects in the PBMC subset, the blood samples were taken before Vaccination 1 and 1 week, 1 month, and 6 months after Vaccination 1. For Stage 2 subjects in the PBMC subset, the blood samples are taken before Vaccination 2 and 1 week, 1 month, and 6 months after Vaccination 2. For the RSV Vaccine Month-0, Month-2 Cohort PBMC subset, the blood samples are taken before Vaccination 1, 1 week and 1 month after Vaccination 1, 2 months after Vaccination 1 (or before Vaccination 2), and 1 week and 1, 6, and 12 months after Vaccination 2.

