3.4. Baseline Variables

3.4.1. Baseline Definition

Day 1 is defined as the day of Vaccination 1. Measurements or samples collected prior to Vaccination 1 on Day 1 are considered the baseline data for the assessments.

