6.2.2.2. Additional Analysis

For the Primary Study Cohort - Stage 1, the seroprotection rate before Vaccination 1 and 1 month after Vaccination 1, and seroconversion rates from before Vaccination 1 to 1 month after Vaccination 1, will be summarized with n, percentage (%), and 2-sided 95% CI, among the evaluable immunogenicity population.

For the Primary Study Cohort - Stage 2, GMTs before and 1 month after Vaccination 2 and GMFRs from before to 1 month after Vaccination 2 will all be descriptively summarized with associated 2-sided 95% CIs by vaccine group for each influenza strain tested. The seroprotection rate before Vaccination 2 and 1 month after Vaccination 2, and seroconversion rates from before Vaccination 2 to 1 month after Vaccination 2, will be summarized with n, percentage (%), and 2-sided 95% CI. RCDCs for each influenza strain testing at the 2 time points (before Vaccination 2 and 1 month after Vaccination 2) will be generated by vaccine group.

The following comparisons will be made in order to assess the interference of RSV vaccine's coadministration with the SIV immune response:

For the **Primary Study Cohort - Stage 1**, GMTs for the groups including SIV coadministration with RSV vaccine dose/formulation at 1 month after Vaccination 1 will be compared with the SIV-only (with placebo) group, for each influenza strain tested. GMRs and associated 2-sided 95% CIs will be calculated.

For the **Primary Study Cohort - Stage 2**, GMTs for the groups including SIV coadministration with RSV vaccine dose/formulation at 1 month after Vaccination 2 will be compared with the SIV-only (with placebo) group, for each influenza strain tested. GMRs and associated 2-sided 95% CIs will be calculated.

All analyses will be performed among the evaluable immunogenicity population.

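### The GMRs leave out the scheduled pre-vaccination titer: Stage 1 intervals are wider than needed unless baseline-to-post correlation is low, and cross-cohort GMRs are open to baseline bias

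*SAP*

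**What the plan says.** SAP 5.2.2.3 gives one GMR method for the whole study: it is "calculated by transforming the group mean difference of the antibody levels in natural logarithm scale to original scale", with a two-sample Student t interval. Protocol 9.2.2 uses the same estimator for the influenza-interference question: "The GMR will be calculated as the group mean difference of logarithmically transformed antibody levels and back transformed to the original units". The Statistical Methods part of the protocol summary likewise bases group and cohort comparisons on ratios of postvaccination GMTs.

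The baseline value is scheduled. SAP 2.2: "For Stage 1 subjects, blood samples were taken before Vaccination 1 and 1, 3, 6, and 12 months after Vaccination 1". SAP 3.4.1: "Measurements or samples collected prior to Vaccination 1 on Day 1 are considered the baseline data for the assessments". It enters the analysis through pre-vaccination GMTs, within-group fold rises, reverse cumulative curves, and seroprotection and seroconversion rates. No covariate model and no between-group contrast of fold rises is planned.

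The GMRs are used in these places:
- SAP 6.2.1.2, RSV neutralizing titer (NT): adjuvant contrasts within Stage 1, and a contrast between cohorts to "Assess SIIV coadministration interference to immune response induced by RSVpreF" 240 µg + CpG/Al(OH)₃.
- SAP 6.2.2.2, HAI: "GMTs for the groups including SIV coadministration with RSV vaccine dose/formulation at 1 month after Vaccination 1 will be compared with" the placebo-plus-SIIV group. SAP 6.3.5 repeats this for H3N2.
- SAP 6.3.3, prefusion F IgG: "GMCs at 1 month after Vaccination 1 for IgG A and IgG B will be compared between the" same two 240 µg CpG/Al(OH)₃ groups, one from each cohort.

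**The concern.** GMRs are the only planned between-group estimates on the titer scale. The other between-group analyses are differences in seroprotection and seroconversion rates (Protocol 9.2.2) and Wilcoxon tests on the cellular assays (SAP 5.2.2.5, 6.3.1). The GMRs carry the adjuvant and interference questions, and SAP 7.2 says the interim results will be used to choose dose, formulation and schedule. Stage 1 has about 31 subjects per arm instead of the planned 39 (Protocol Table 4).

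Two different things are at stake. Within Stage 1, randomization makes the unadjusted GMR unbiased, so the cost is interval width. Between cohorts there is no such protection. Stage 1 enrolled from April to June 2019, whereas the Month-0, Month-2 Cohort was added by Amendment 3 and randomized separately. A difference in pre-vaccination titer between the two groups passes into the GMR. That contrast is this study's only planned estimate of whether SIIV affects the RSV response.

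**Working it through.** **The plan's own figure.** The documents state no GMR precision. The only sample-size figures are in Protocol Table 11. For a 5% event rate and 31 subjects, 1 − 0.95³¹ = 0.796, which agrees with the stated 80%; the other cells of that table also reproduce.

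**Inputs.** n = 31 per arm (Protocol Table 4); two-sided 95% intervals (SAP 6.2.1.2). The correlation ρ between log baseline and log post-vaccination titer is not given, so a range is used. The model is bivariate normal with equal SDs.

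**Interval width within Stage 1.** The expected width on the log scale, two-arm ANCOVA relative to the unadjusted t interval, is

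W = [t(0.975, 2n−3) / t(0.975, 2n−2)] × √{(1 − ρ²)(1 + 1/(2n−4))}.

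This charges ANCOVA for the lost degree of freedom and for chance baseline imbalance. At n = 31 the terms without ρ are (2.0010/2.0003) × √(1 + 1/58) = 1.0089. For ρ = 0.5, W = 1.0089 × √0.75 = 0.874.

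| ρ (assumed) | W, all baselines valid | Unadjusted n per arm giving the same width | W, 29 of 31 baselines valid per arm |
|---|---|---|---|
| 0 | 1.009 | – | 1.045 |
| 0.13 | 1.000 | 31 | – |
| 0.2 | 0.989 | – | 1.024 |
| 0.3 | 0.962 | 33.4 | 0.996 |
| 0.5 | 0.874 | 40.3 | 0.905 |
| 0.7 | 0.721 | 58.8 | 0.746 |

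The last two columns come from simulation (60,000 runs per ρ). The simulated values of W with complete baselines agree with the formula to within 0.001, and coverage was 0.949 to 0.951 for both methods. A ρ of 0.47 gives the width of an unadjusted comparison with 38.9 per arm, about the original 39.

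**On the ratio scale.** With an assumed ln-SD of 1.0, the unadjusted limits are GMR ×/÷ exp(2.0003 × √(2/31)) = ×/÷ 1.66. After adjustment they are ×/÷ 1.63, 1.56 and 1.44 at ρ = 0.3, 0.5 and 0.7.

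**Fold rises as an alternative.** A ratio of fold rises is not equivalent. With equal SDs its relative width is √{2(1 − ρ)}: 1.18 at ρ = 0.3 and 1.00 at 0.5. It is therefore wider than the unadjusted interval below 0.5.

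**Cross-cohort bias.** If log post-vaccination titer rises with log baseline at slope β, the unadjusted GMR is multiplied by (baseline GMT ratio)^β. Both quantities are assumed:
- ratio 1.25: 1.25^0.3 = 1.069, 1.25^0.5 = 1.118, 1.25^0.7 = 1.169;
- ratio 1.5: 1.5^0.3 = 1.129, 1.5^0.7 = 1.328.

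**The case against.** The Stage 1 part can be called a preference. The planned GMR is unbiased, declared consistently in both documents, and equal to the ratio of the tabulated GMTs when the same subjects are used. The study is descriptive and sets no GMR precision target, so neither 39 nor 31 was chosen for this purpose. The gain depends on an unstated ρ: at 0.3 it is 4%, and it vanishes if 2 of 31 per arm lack a baseline. The calculation also ignores values set at half the LLOQ or at the ULOQ. All of this stands as a limit on size. It does not remove the point, because a study that relies on estimation is judged by its intervals, and with complete baselines the worst expected cost is about 1%.

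Baseline GMTs and within-group fold rises are reported, so a reader could see an imbalance. That is true, but they yield no adjusted contrast or interval.

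The cross-cohort bias is hypothetical: no baseline difference is reported, and the cohorts share an age range and nearly all eligibility criteria. Adjustment would also be partial. The evaluable sets differ, since Stage 1 needs the one-month draw after Vaccination 1 (SAP 4.1.2) while the other cohort needs both doses and the draw after Vaccination 2 (SAP 4.3.2). This stands and belongs in the caveat.

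Timing is the strongest practical objection. Protocol 5.1.2 keeps the sponsor team blinded only until one-month data are available, and SAP version 2 is dated June 2020, a year after Stage 1 enrollment ended. Stage 1 results may already be known. This limits how the adjusted GMR may be presented, not whether it is useful.

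**Conclusion.** The concern holds. No planned GMR uses the baseline titer. Within Stage 1 this is a loss of precision, not of validity: nothing at a correlation of about 0.13 or less, 4% of interval width at 0.3, 13% at 0.5 and 28% at 0.7, and less if baselines are missing. The size cannot be fixed from the documents, because it rests on an assumed correlation, normality and equal SDs.

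For the cross-cohort NT and IgG GMRs the issue is possible bias. It is a factor of 1.07 to 1.17 for an assumed baseline ratio of 1.25 and slopes of 0.3 to 0.7. No such difference has been shown, but the design does not protect against one. The change should be made; the plan is not invalid without it.

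**What to change.** - **Stage 1 GMRs.** In SAP 5.2.2.3, take the GMR and 95% interval from an ANCOVA of ln post-vaccination titer on vaccine group and ln pre-Vaccination 1 titer of the same assay or strain. Apply it in 6.2.1.2, 6.2.2.2 and 6.3.5.
- **Which arms share a model.** For HAI and H3N2 every arm receives SIIV, so all eight arms may share one model. For the RSV NT adjuvant contrasts, fit only the two arms compared or only the RSV-vaccinated arms, because the baseline slope under placebo may differ.
- **Unadjusted GMR.** Keep it as supportive. The evaluable population asks only that subjects "Have at least 1 valid and determinate assay result for the 1-month post-Vaccination 1 visit", so those without a valid baseline drop out of the adjusted model but remain here.
- **Cross-cohort NT and IgG (6.2.1.2, 6.3.3).** Also report a baseline-adjusted GMR. State that the comparison is not randomized and that adjustment does not remove other cohort differences, including the different evaluable-population rules.
- **Stage 2.** Leave as planned, because the pre-Vaccination 2 titer is measured after randomized treatment.
- **Protocol 9.2.2.** Align the wording.

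The cost is SAP text and one standard model. SAP section 2 allows the change, since no primary endpoint is affected. If Stage 1 one-month data are already unblinded, label the adjusted GMR as added after unblinding, so that the reader knows the unadjusted one was prespecified.
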